### **1.3 Summary of Clinical Experience**

In 2016, Click conducted an 8-week, open-label, single-arm, blinded clinical trial in which 416 subjects were enrolled. All study procedures were reviewed and approved by Western Institutional Review Board. The trial was registered with clinicaltrials.gov (NCT02656745) (Iacoviello et al., 2017).

**Rationale:** The goal was to initiate the process of gaining clinical validation for Clickotine by gaining data to guide improvements to the product and the design of further efficacy studies.

**Aims:** The primary aim was to assess engagement with Clickotine, hypothesized to be key to its effectiveness. Secondary aims were to assess Clickotine’s effect on smoking behavior, its relationship to engagement, and the safety and tolerability of the digital therapeutic.

**Results:** The aims of the pilot were successfully met, recruiting 416 subjects in a three-month period and completing the trial in five months. Results were summarized as follows:

**Recruitment, enrollment, and retention:** Social media advertisement for current smokers interested in using a smartphone app to help quit proved effective in recruiting subjects. The average cost of advertisement was \$28.91 per participant enrolled. Subjects had a mean age of 36 and an average of 6.1 on the Fagerstrom Test for Nicotine Dependence, with 18.1 years of smoking history and 16.7 cigarettes per day. The 87.7% retention rate was akin to other web-based smoking cessation trials with similar recruitment methods (Bricker et al., 2014; Munoz et al., 2009; Bricker et al., 2017).

**Engagement:** Subjects opened the Clickotine app (a standard and important metric for measuring engagement with a digital therapeutic) an average of 100.5 times. This translates to 1.8 app opens

per day over the course of 56 days. However, the app was engineered to emphasize active use (requiring app opens) during the period prior to the target quit date; in the week before target quit date, users opened the app 3.2 times per day.

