## **6.2 iCO Smokerlyzer**

Participants will receive an iCO Smokerlyzer to be used at the user's discretion periodically throughout the trial regardless of treatment group. At Week 4 (Day 28), participants will be asked to submit an exhaled CO assessment to ensure the Smokerlyzer works properly, to identify any issues and as an adherence check. At the time of the Outcome Survey, participants will be required to submit another exhaled CO assessment, which will be recorded as a study endpoint.

Upon completion of the Outcome Survey, participants will be invited to submit the CO assessment over a live video feed to confirm identity, until videos are received from 25 CKT users and 25 QG users. After 25 videos are received from each treatment group, participants will no longer be invited to submit the CO assessment over live video feed and will instead receive a reminder to remotely submit an exhaled CO assessment.

In order to conduct the CO assessment via live video monitoring, participants must have access to another device with video capabilities, such as another mobile device or computer. Participants that are invited to conduct the CO assessment via live video monitoring will consent to participate in live video monitoring at the end of the outcome survey by answering "Yes" or "No". Study participants that answer "Yes" and will then be linked to schedule a video call via Calendly with the research coordinator. Participants will have the option to select their preference of video platform on Calendly.

During the live video monitoring participants will be required to provide a personal ID to confirm identity. Participants who consent to participate in the live video CO assessment will receive an additional \$50 Amazon gift card for their participation.

Those who do not consent to participate in the live video monitoring CO assessment will receive a reminder to submit the end of study CO assessment.

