#### **10.4 Secondary Endpoint**

Concordance rates between self-reported 30-day abstinence and the remote CO monitoring result will be estimated, with concordance > 85% considered evidence of a valid reporting process by Magellan Behavioral Health. Concordance rates will be compared between users that submit the CO measurement under video monitoring and those that do not. Upon completion of the Outcome Survey, participants will be invited to submit the CO assessment over a live video feed to confirm identity, until videos are received from 25 CKT users and 25 QG users. After 25 videos are received from each group, participants will no longer be invited to submit the CO assessment over live video feed.

Secondary analysis of the subgroup of NRT/pharmacotherapy users will be conducted to compare cessation rates between the CKT+NRT group and the CKT-only group, to confirm the initial trial result that CKT+NRT is not superior to CKT-alone.

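### The video versus non-video CO concordance comparison sets volunteers against decliners and later completers, so it cannot by itself show validity or the value of video

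*Protocol*

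**What the plan says.** Protocol 6.2, 8.2 and 10.4, and SAP 10.4, describe one procedure. People who finish the Outcome Survey are invited to give the week-8 CO reading on live video. Invitations run "until videos are received from 25 CKT users and 25 QG users. After 25 videos are received from each group, participants will no longer be" asked. Section 6.2 repeats the stop: "After 25 videos are received from each treatment group, participants will no longer be invited to submit the CO assessment over live video feed".

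Video is opt-in. Under 6.2, those invited "will consent to participate in live video monitoring at the end of the outcome survey by answering" yes or no, which in Appendix 15.4 comes after the smoking-status questions. The same section says that "participants must have access to another device with video capabilities", asks for personal identification, and adds a $50 gift card. People who decline are reminded to send the ordinary unsupervised reading, as is everyone who finishes after the quota is full.

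The planned analysis in 10.4 is: "Concordance rates will be compared between users that submit the CO measurement under video monitoring and those that do not". No section randomises the invitation, separates decliners from people never asked, or adjusts this comparison for completion order or recruitment source.

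Two conclusions are attached to it. Protocol 2.2 expects no significant difference and treats that as showing that both self-report and remote verification are valid. The SAP's Data Analysis Plan uses the comparison to judge what video monitoring adds.

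**The concern.** A comparison of video with non-video readings answers the plan's question only if the two groups would have had similar concordance without video. The invitation rule does not provide that. Every video reading comes from someone who agreed to be watched. Every non-video reading comes from someone who was asked and gave no video, or who finished after the quota filled.

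The first contrast is the more worrying one. The offer follows the report of smoking status and involves an identity check. Someone who has just misreported abstinence has a reason to decline. Access to a second device and interest in the payment also select. Acceptance may therefore be related to the quantity being compared.

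The error can go either way. Selection could create a gap that is credited to video. It could also mask a real one, which 2.2 would then read as validity. The SAP's summary of the protocol links remote verification to reimbursement, so the conclusion has a use beyond the trial.

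**Working it through.** **The plan's own figures.** The quota of 25 per arm has no stated calculation, so there is nothing to reproduce. The 78 per arm, used below as an input, does reproduce. With rates 0.262 and 0.083 (mean 0.1725) and a two-sided pooled z test:

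- SE under the null = √(2 × 0.1725 × 0.8275 / 78) = 0.0605
- SE under the alternative = √((0.262 × 0.738 + 0.083 × 0.917) / 78) = 0.0588
- z = (0.179 − 1.96 × 0.0605) / 0.0588 = 1.03, power 84.8% against the stated 85%.

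**Inputs.** 78 per arm (10.5); retention 87.7% (pilot, Protocol 1.3; assumed to carry over); quota 25 per arm (10.4). Uptake *a*, the share of invited people who give a video, is not in the documents and is varied. It is taken as constant over time and equal between arms. Each arm stops at its own quota, and every completer is assumed to send a CO reading.

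**Step 1: who is in the non-video group.** Completers per arm *m* = 78 × 0.877 = 68.4. Invited = min(*m*, 25/*a*). Decliners = invited − videos. Never invited = *m* − invited.

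| Uptake | Invited per arm | Decliners | Never invited | Non-video group |
|---|---|---|---|---|
| 100% | 25.0 | 0 | 43.4 | 100% later completers |
| 75% | 33.3 | 8.3 | 35.1 | 19% decliners, 81% later |
| 50% | 50.0 | 25.0 | 18.4 | 58% decliners, 42% later |
| 36.5% | 68.4 | 43.4 | 0 | 100% decliners |

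The quota binds only if *a* exceeds 25/68.4 = 36.5%. At full retention the threshold is 25/78 = 32%, and at 80% retention it is 25/62.4 = 40%. At or below it everyone is invited and the contrast is purely accepters against decliners. No uptake yields a comparable control group.

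**Step 2: size of a selection effect (illustration).** Assume overall concordance 85%, acceptance 55% among concordant and 25% among discordant people, and no effect of video.

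- Uptake = 0.85 × 0.55 + 0.15 × 0.25 = 0.505
- Video group: 0.4675 / 0.505 = 92.6% concordant
- Decliners: 0.85 × 0.45 / 0.495 = 77.3%
- Invited = 50 / 0.505 = 99, so 49 decliners; never invited = 136.8 − 99 = 38, at 85%
- Pooled non-video: (49 × 0.773 + 38 × 0.85) / 87 = 80.6%

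The result is a 12-point gap due to selection alone. The never-invited group, reported separately, would show the true 85%.

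**Step 3: precision.** With 50 video and 87 non-video at 85% concordance, the 95% half-width for the difference is 1.96 × √(0.1275 × (1/50 + 1/87)) = 12.4 points. Power for a 10-point difference is about 32% (90% versus 80%) or 27% (85% versus 75%). Even without selection, a non-significant result would say little.

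**The case against.** The best defence is about context. This is a Phase I study whose stated aim here is feasibility, the video subset serves to confirm identity and check the process, and the primary endpoint is self-report, which the video rule does not touch. That limits the weight of the point. It does not remove it, because Protocol 2.2 and the SAP attach conclusions about validity and value to this comparison.

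A second defence is that poor precision is the larger problem. Precision is indeed poor, but a larger sample would not remove selection. Third, recording is partly in place: Outcome Survey question 24 already captures yes or no from those invited. What is missing is an explicit invitation status for everyone and separate reporting.

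Three stronger readings are tempting, and the documents do not support them.

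- **That video covers all early completers and no late ones.** The rule governs invitations. Only accepters give a video, and late completers go uninvited only if uptake exceeds about 36.5%. The SAP's Data and Safety Monitoring Plan does describe the subset as the first 50 completers, which differs from the quota wording and should be reconciled with it.
- **That the video group would be mostly social-media recruits.** The pilot's pace ("recruiting 416 subjects in a three-month period") does not give this trial's accrual by source. The SAP timetable has one recruitment window for all advertising. If the mailing to 11,000 network members went out in one burst, the imbalance could reverse; at equal pace it is zero.
- **That the 85% benchmark is compromised.** Section 10.4 ties that benchmark to overall concordance between self-report and remote CO. It does not tie it to the video contrast.

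**Conclusion.** The point holds for the planned video versus non-video comparison and only for that. Under the written rule the non-video group is invited decliners, never-invited later completers, or a mix, at every uptake. This follows from the text and needs no assumed figure. The shares in the mix rest on the pilot's retention and on an uptake that the documents do not give.

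The 12-point gap shows what a plausible link between acceptance and concordance could do; it is not a forecast. If acceptance and completion order are both unrelated to concordance, the bias is zero, but the planned analysis could not show that. The comparison therefore cannot by itself support the inference in Protocol 2.2 or the judgement on video in the SAP's Data Analysis Plan. This is a secondary analysis in a feasibility study, and the remedy is mainly one of recording, reporting and wording.

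**What to change.** 1. Record for every completer whether an invitation was issued and its result: video given, invited without video, or never invited.
2. In Protocol 10.4 and SAP 10.4, report concordance separately for those three groups, and by recruitment source, with differences and 95% confidence intervals.
3. State there, in Protocol 2.2 and in the SAP's Data Analysis Plan, that the pooled video versus non-video contrast is descriptive and is not evidence of validity or of what video adds.

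The cost is a status flag and a few sentences; enrolment, payments and the quota stay as they are. The drawback is small groups. With the Step 2 numbers at 85% concordance, the half-width is about 14 points for video versus decliners (50 versus 49) and 15 points for video versus never-invited (50 versus 38), and wider within recruitment source.

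Optionally, invitations could be spread at random over the whole completion period, within arm and recruitment source. That makes invited versus never-invited a randomised comparison, but it should only be supporting, because refusals dilute it. Inviting 3 in 4 of 137 completers gives about 103 versus 34. At 50% uptake a true 10-point effect shrinks to 5 points (85% versus 80%), for which power is about 12%, against about 32% for 90% versus 80% in the planned 50 versus 87. The video count would also no longer be fixed at 25 per arm.

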#### **10.5 Sample Size**

Power analysis: Estimated ITT 30-day cessation rates after 8-weeks of use for CKT and QG are based on published reports: CKT 26.2%, QG 8.3%. A power analysis for logistic regression using g\*Power 3.1 software was conducted with the following parameters: 85% power to detect a group difference with  $\alpha = 0.05$  two-sided significance level, and estimated Group 1 proportion,  $p_1$ , of 0.262 and a Group 2 proportion,  $p_2$ , of 0.083. A sample size of 78 subjects in each group will yield 85% power to detect such a difference. To obtain this sample size, we plan to obtain consent from 195 subjects and enroll 156 into the study by downloading the assigned app, which reflects a conservative approach to the retention rate observed in our pilot data.

### **11. QUALITY CONTROL AND QUALITY ASSURANCE**

#### **11.1 Data Collection**

Data collection during the 8-week study will occur through the Baseline Survey, Smokerlyzer Confirmation (Day 28), the Outcome Survey at 8 weeks and the iCO Smokerlyzer assessment.

Primary outcome data, including covariates to be included in regression analyses, are acquired via the web-based baseline survey and outcome survey. Data are conveyed via an automated process from the web-based survey into a format matching the study database. Research coordinator is responsible for entering the survey data into the study database within 72 hours of survey completion.

Secondary outcome data: 1) CO readings are automatically conveyed via email by the iCO Smokerlyzer App to the study coordinator, who will enter the result into the database (a numerical value in parts-per-million (ppm; <7 ppm is defined as evidence of cigarette abstinence); 2) self-reported NRT and smoking cessation pharmacotherapy use (including e- cigarette use) will be acquired via the outcome survey.

## **11.2 Audit and Inspection of the Study**

No audit or formal Inspection of the study is planned.

# **12. ETHICS**

## **12.1 Regulatory Considerations**

As this study utilizes solely commercially available Apple iPhone and Google Play Store devices, and does not involve any medical recommendations regarding use of prescription or over the counter quit aids, this study is subject to Investigational Device Exemption (IDE).

This study is funded by a National Institute of Health, National Institute of Drug Abuse grant 1 R43 DA045395-01 “Clinical trial of an innovative digital therapeutic for smoking cessation with biochemical verification” to [name]. The PI will seek NIDA prior approval for any significant changes proposed to the protocol. All Western IRB actions relevant to the study, including changes or amendments to the study protocol, will be communicated to NIDA.

## **12.2 Institutional Review Board or Independent Ethics Committee**

Before this study begins, the protocol will be submitted for IRB review. IRB approval will be obtained prior to any screening or recruitment activity.

## **12.3 Informed Consent**

The sponsor and delegates will fully inform potential participants of pertinent aspects of the study, via the “Informed Consent Form” (See Appendix 14.1). This informed consent will be obtained by electronic communication prior to the conduct of any study-specific procedures. Opportunities to

ask questions by email or telephone are provided prior to signing informed consent. The participant will receive a copy of the signed informed consent.

#### **12.4 Withdrawal of Consent for Continued Study Participation**

Participants will be instructed that they are free to withdraw from the study at any time without penalty or implications for any healthcare they receive. Participants who terminate the study early for any reason.

### **13. FINANCING AND INSURANCE**

Funding for this study is provided by the National Institutes of Health / National Institute of Drug Abuse grant 1 R43 DA045395-01 “Clinical trial of an innovative digital therapeutic for smoking cessation with biochemical verification” (PI: [name].).

Click Therapeutics shall maintain, at all times, the following insurance coverages:

- a) Commercial general liability insurance for bodily injury and property damages of \$2 million for each occurrence and \$4 million in the aggregate for policy year;
- b) Errors and omissions including coverage for data breach and cyber liability of \$1 million per occurrence and \$3 million in the aggregate for policy year;
- c) Workers compensation insurance as required by law;
- d) All policies shall be written using at least A- carriers falling within a “Secure rating” by the A.M. Best Company or its replacement

## 15.2 Eligibility Questionnaire

*"If the answer to any of questions 2 -8 is "no" or if question 9-10 is "yes", the user is not eligible for the study"*

### My Digital Study Eligibility Survey

This survey will determine if you are eligible to participate in the study and includes basic questions about your smoking history. Your answers to the eligibility survey questions will be entered in this secured website and kept confidential by the My Digital Study Team.

**1. Please enter your:**

Full name: \_\_\_\_\_ Email address: \_\_\_\_\_

**2. Do you smoke at least 5 cigarettes a day?**

- YES
- NO

**3. Are you interested in quitting in the next 30 days?**

- YES
- NO

**4. Do you have access to an iPhone with iOS 9 or greater capabilities, or an Android with OS 7 or great capabilities?**

- YES
- NO

**5. Are you between 18- 65 years old?**

- YES
- NO

**6. Do you currently live in the United States?**

- YES
- NO

**7. Are you willing and able to receive email & SMS (text messages)?**

- YES
- NO

**8. Do you have internet access to download treatment while on the phone with the research coordinator?**

- YES
- NO

**9. Are you currently using a mobile phone-based smoking cessation intervention?**

- YES
- NO

**10. Are you currently using a nicotine replacement therapy (nicotine patch, gum, inhaler, nasal spray, or lozenge)?**

- YES
- NO

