### **4.3 Exclusion Criteria**

1. Prior use of Clickotine or QuitGuide.
2. Current use of pharmacotherapy for smoking cessation or nicotine replacement therapy (NRT).

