## **6.4 Permitted Concomitant Treatments**

To control for medication or NRT use, participants will not be eligible to enroll if they are currently using a medication or NRT at study enrollment.

Starting at Day 0 of the study, study participants will be allowed to choose to begin using a smoking cessation medication or NRT. Participants will be asked about medication or NRT use during the study in outcome survey.

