### **7.1 Recruitment, Screening and Baseline Period**

Advertisements (See Appendix 15.18) will be placed on social media and sent to 11,000 participants in a Magellan Behavioral Health value-based care network. Respondents to the advertisements will be directed to a website that asks several questions to determine their eligibility to participate in the study (See Appendix 15.2). If answers indicate eligibility, the user will be prompted to review and sign the informed consent. Participants are instructed to contact the study coordinator via telephone or email to answer any questions that the participant has, and/or to further discuss the study prior to completing the online Informed Consent form. Upon completion of the online Informed Consent, a copy of the signed ICF will be provided to the participant.

After the informed consent is signed, each participant will be assigned a unique participant user ID that will be used for the duration of the study. Once participant user ID numbers have been assigned, they cannot be reassigned or reused for any reason. The investigator and research coordinator must maintain a log linking the participant user ID to the participant's name. The investigator and study coordinator must follow all applicable privacy laws in order to protect a participant's privacy and confidentiality.

After signing the online informed consent, participants will automatically receive the Baseline Survey via email. The online Baseline survey (See Appendix 15.7) must be completed within 7 days (*Ex. Criteria #3*) as the participant's personal Baseline survey link expires 1 week after the automated email is generated to the study participant. Please see Section 6.3 for the baseline follow-up attempt procedure. Participants who do not complete the Baseline Survey during the 7-day baseline period window will be considered a screen fail and discontinued from the study. Participants that are discontinued from the study will not be eligible for rescreening.

This questionnaire was constructed from several standard surveys measuring smoking and addiction behavior (Modified Cigarette Evaluation Questionnaire, Capelleri et. al 2007; Mood and Physical Symptom Scale, West and Hajek, 2004; Morisky Medication Adherence Scale, MMAS-4,

Morisky et. al 1986), as well as basic medical history and demographic questions for data purposes (Cappelleri, et. al, 2007)

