### **Step 1: Research coordinator confirms eligibility and randomizes**

- Study coordinator reviews baseline questionnaire answers with participant to confirm eligibility
- After study eligibility is confirmed, the study coordinator will randomize the participant into one of the two treatment groups (Clickotine or QuitGuide)
- The assigned treatment and iCO Smokerlyzer application links will be emailed to the participant for download. The study coordinator will provide step-by-step application download instructions for the participants over the phone call and explicitly written out in the email. The participants who are randomly assigned to Clickotine will receive an access code in the email that contains the application download instructions because Clickotine requires a valid access code for the user to partake in the program.

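### The printed eligibility form does not match section 4.3: it has no item for cessation medicines or for past use of Clickotine or QuitGuide, and no later form supplies one

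*Protocol*

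**What the plan says.** Protocol section 4.3 has two exclusions: "Prior use of Clickotine or QuitGuide" and "Current use of pharmacotherapy for smoking cessation or nicotine replacement therapy (NRT"). Section 6.4 leans on the second to control for medication: "participants will not be eligible to enroll if they are currently using a medication or NRT at study enrollment". From Day 0 onward, participants may start either kind of aid.

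The working screen is the web questionnaire in 15.2. A No to any of questions 2–8, or a Yes to 9 or 10, means that "the user is not eligible for the study". Two of its items bear on the exclusions:

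- Question 9: "Are you currently using a mobile phone-based smoking cessation intervention"
- Question 10: "Are you currently using a nicotine replacement therapy (nicotine patch, gum, inhaler, nasal spray, or lozenge"

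Eligibility is checked again on the randomization call (7.2, 7.7). The one activity listed for that check, in 7.8 Step 1, is: "Study coordinator reviews baseline questionnaire answers with participant to confirm eligibility".

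At Week 8, outcome survey questions 10 and 11 (15.4) ask which quit aids the participant is taking at that time. The product list includes varenicline and bupropion.

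**The concern.** A screening form should be able to apply the criteria it serves. Here the stated rule, followed exactly, admits two kinds of people whom 4.3 excludes and rejects a third kind whom it does not exclude.

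Two things are at stake. First, section 6.4 treats enrolment as free of cessation medicines, and the comparison of CKT+NRT with CKT-only (10.4) relies on that for its meaning. If someone already on a medicine enters and is still taking it at Week 8, the data cannot distinguish that person from one who began during the trial. Second, someone who has already used one of the two apps has had part of a study treatment beforehand. Compliance with either exclusion could not be fully shown from the printed forms.

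**Working it through.** **1. Criteria against the web form**

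| Criterion | Item in 15.2 | Who can truthfully pass | Who is rejected without a criterion |
|---|---|---|---|
| Past or current use of either study app (4.3) | Q9, current use of any phone-based programme | A past user of either app who has stopped | A current user of an unrelated app |
| Current cessation medicine (4.3) | None | A current varenicline or bupropion user | – |
| Current NRT (4.3) | Q10, five product forms | No current user of a listed form | – |
| Current e-cigarette use (exclusion in the SAP file only) | None | A current e-cigarette user | – |

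**2. Later checks**

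- Baseline survey (15.3). Printed items run from 7 to 31. None asks about cessation medicines, NRT or earlier app use. Items 1–6 are not shown. Section 7.1 says the survey draws on the "Morisky Medication Adherence Scale, MMAS-4", but adherence items of that kind are printed only in the outcome survey (questions 12–15).
- Randomization call. The listed content is a review of those baseline answers, so the forms give the coordinator nothing to review on these points. Section 7.7 allows up to 7 + 3 = 10 days from the baseline link to the call.
- Pre-screening call. It appears only in the SAP file's protocol summary, with no listed questions. Protocol 7.1 and 7.6 go from the web form straight to consent.

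**3. Outcome data.** Questions 10–11 record use at Week 8 without a start date. Use that began before Day 0 and continues is merged with use begun on study. Someone who stopped before Week 8 would answer No and be grouped as CKT-only.

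**4. Size for the primary comparison.** Inputs from section 10.5: p1 = 0.262, p2 = 0.083, n = 78 per arm, two-sided α = 0.05, stated power 85%. With p̄ = 0.1725:

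power = Φ{[(p1 − p2) − 1.96·√(2p̄(1 − p̄)/n)] / √([p1(1 − p1) + p2(1 − p2)]/n)}

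= Φ{(0.179 − 1.96 × 0.0605)/0.0588} = Φ(1.03) = 84.8%.

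The same method asks for 79 per arm, so the plan's figure is reproduced, and correcting the forms would not change it.

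The documents give no prevalence of medicine use at enrolment, so what follows is illustration. Suppose a share q of each arm are unscreened medicine users who quit at rate r, or at the arm's planned rate if that is higher. Each arm's rate becomes (1 − q)·p + q·max(r, p). For q = 5% and r = 0.30 this gives 0.95 × 0.262 + 0.05 × 0.30 = 0.264 and 0.95 × 0.083 + 0.05 × 0.30 = 0.094, with power 79.7%. Over r = 0.20 to 0.40:

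| q (assumed) | Expected of 156 | Per arm | Power |
|---|---|---|---|
| 2% | 3.1 | 1.6 | 82.5–83.6% |
| 5% | 7.8 | 3.9 | 78.8–81.8% |
| 10% | 15.6 | 7.8 | 72.3–78.5% |

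**The case against.** The strongest reply is that the web form is not the only safeguard. Section 4.2 wants eligibility reviewed and documented by a qualified team member. The schedule in 7.5 marks eligibility at screening, baseline and randomization, 7.2 requires verification on the day of the call, and the SAP file adds a pre-screening call. Naming one activity on the call does not mean nothing else is asked, and baseline items 1–6 might cover the gap. This stands in part: detection is undocumented, not ruled out. A reader might infer that breaches must go unnoticed, or that the study never asks; the documents do not support going that far.

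Nor do they support saying that neither exclusion is screened. Question 10 covers NRT, and question 9 catches current users of either study app.

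A reader might also infer that the primary result would be biased towards one arm. Both arms are screened in the same way before 1:1 randomization, so any leakage is balanced in expectation. Aids are permitted from Day 0 and section 6.5 excludes none, so medicine-aided quits are part of the primary endpoint by design. What remains is dilution or chance imbalance.

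Finally, it is tempting to state what fraction of the CKT+NRT group could be pre-enrolment users. That needs two prevalences, neither of which is given, plus the share still on treatment at Week 8. Any such fraction would rest on assumption alone. The number of past app users among entrants is likewise unknown.

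**Conclusion.** The mismatch is real on the printed text and goes beyond missing detail, because the eligibility rule applied as written contradicts 4.3 in both directions. The gaps are specific: current cessation medicines and past use of either study app.

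The direct analytic consequence is confined to the secondary CKT+NRT versus CKT-only comparison, which is already a comparison of self-selected users. For the primary comparison the direction is loss of power, and its size cannot be fixed from the documents. The power figures shown also assume that the planning rates contain no such users, which the documents do not establish. The conclusion depends on unseen baseline items 1–6 not asking these questions and on the coordinator having no prescribed questions beyond the printed steps. Severity is moderate.

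**What to change.** 1. Reword question 10 to ask about current use of NRT or any medicine to help stop smoking, using the product list already in outcome question 11.
2. Replace question 9 with an ever-use item listing several cessation apps, with Clickotine and QuitGuide among them. The other names keep the item from revealing which apps are under test.
3. Reconcile question 9 with 4.3 on current use of other apps: either the form stops rejecting those people or 4.3 says that they are excluded. Reconcile 4.3 with the SAP file on e-cigarette use, and make question 10 follow.
4. Have the coordinator ask both items again on the Day 0 call, before randomization, and record the answers. Adding them to the baseline survey alone would miss an aid started between that survey and the call. With a Day 0 record, use reported at Week 8 can be read as begun on study. Aids stopped before Week 8 would still be missed.

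The cost is two reworded web items, two recorded questions on an existing call and a minor amendment, with slightly more screen failures.
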